5.4 Consent

Cognitive Interviews: Written informed consent will be taken by the Research Associate at the time of the interview.

Focus Groups: Written informed consent will be taken by the Research Associate at the time of the focus group.

5.4.1 Withdrawal of Consent

Participants have the right to withdraw from the study at any time, for any reason and without giving a reason. If the family member decides to stop part way through the interview, they will be asked if the data already collected may remain in the study for analysis.

5.5 Adverse Events

In the highly unlikely event of a participant becoming unwell or injuring themselves during their participation in this study the research Associate will notify the local PI, who will then notify the Sponsor and the REC as required. Participants in the interviews and focus groups will be reassured that they need not discuss anything they find distressing and that the interview will be temporarily or permanently halted if they become very upset. If the family member indicates the need for on-going help/support the Research Associate will direct them towards their own General Practitioner in the first instance and will also notify the CI.

5.6 Data Management

At the time of consent, the participants in the cognitive interviews or focus groups will be allocated a unique study number. This will be used, along with their initials, on the consent form and any other study documentation. All study documentation – screening logs, consent forms, and contact details of family members - will be stored in a locked filing cabinet in a secure office used by the Critical Care Research Teams at the Freeman Hospital and Royal Victoria Infirmary. In transcripts of interviews and focus groups, identifiable data (e.g. names) will be removed or replaced by a pseudonym.

The study documentation from the cognitive interviews and focus groups will be stored securely (locked filing cabinets in rooms with restricted access; password protected computer files) in the Institute of Health and Society, Newcastle University, supervised by [name]. Following transcription and checking of the audio files and completion of the FREE-Qual Study, the audio files from the cognitive interviews and focus groups will be deleted. No data with the

potential to identify participant, patients, staff or hospitals will be transcribed from the audio files. To this end, in transcripts of interviews and focus groups, identifiable data (e.g. names) will be removed or replaced by a pseudonym.

A study Master File will be set-up, containing all the required documentation – protocol, PIS, consent form, Trust R&D approval, REC approval etc. Once the study is completed all study documentation will be archived by the local PI in the Critical Care Research office for a period of 10 years.

All data generated from this study will be stored in accordance with the Data Protection Act 1998.

6. FREE Study

Research Ethics Committee reference:	13/SC/0037
Sponsor reference:	ICNARC/02/06/12
NIHR CRN Portfolio ID number:	13880
Protocol version:	1.2
Protocol version date:	18 October 2013

6.1 Critical care unit inclusion criteria

To take part in the FREE Study, critical care units must fulfil the following inclusion criteria:

- agreement from the Principal Investigator (PI) to recruit up to four family members for consecutive patients staying more than 24 hours;
- provision of timely data on family members on the FREE secure web-based data entry system;
- commitment to recruit participants for a minimum of 12 months (up to a maximum of 17 months);
- active participation in the Case Mix Programme (CMP).

At each participating unit, a PI will be identified and who will be responsible for the conduct of the study locally.

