The overall aim of the FREE Study is to inform valid, representative and cost-effective future use of the FS-ICU questionnaire into quality improvement programmes for adult critical care services in the NHS in the UK.

The objectives of the FREE Study are:

- to test the face and content validity and the comprehensibility of the FS-ICU;
- to establish the internal consistency, construct validity and reliability of the FS-ICU;
- to describe family satisfaction using the FS-ICU and explore how family satisfaction, measured with the FS-ICU, varies by:
 - family member;
 - patient characteristics;
 - unit/hospital characteristics;
 - other contextual factors; and
 - country (through comparison with FS-ICU data held in Canada);
- to model approaches to sampling to achieve representative sampling for feasible, cost effective future use of the FS-ICU in quality improvement in the NHS.

4. Study design

The FREE Study is a mixed methods study comprising a psychometric evaluation (FREE-Qual) leading to a multicentre cohort study.

The objectives of the FREE Study will be addressed in two sub-studies.

FREE-Qual

FREE-Qual is a qualitative study (see: Section 5) which will address the first objective by testing the face and content validity and the comprehensibility of the validated Canadian FS-ICU. Modifications to the FS-ICU questionnaire will then be made, if required.

The FREE Study

FREE is a multicentre cohort study (see: Section 6) which will address the remaining objectives using the UK adaptation of the FS-ICU questionnaire (FREE-Qual).

Staff at twenty adult, general critical care units will identify up to four family members for consecutive patients admitted to their unit who stay more than 24 hours. Family members who consent to take part will be sent a questionnaire three weeks following patient discharge from the critical care unit.

The recruitment period will be one year, chosen to avoid bias from seasonal variation in case mix and workload. A psychometric assessment of the FS-ICU will be undertaken using data collected during the first month.

5. FREE-Qual

Research Ethics Committee reference:	12/YH/0415
Sponsor reference:	ICNARC/02/05/12
NIHR CRN Portfolio ID number:	112459
Protocol version:	1.0
Protocol version date:	31 July 2012

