7.1 Sample size and recruitment rate calculation

The duration of recruitment will be one year, chosen to avoid bias from seasonal variation in case mix and workload. Data from the CMP database indicates that an average of 520 patients are admitted per unit, per year, and of these, 74% stay at least 24 hours, corresponding to 7,700 patients (approximately 19,250 family members). Assuming an average of 2.5 family members per patient and a 66% response rate,¹⁵ a total sample of approximately 12,700 responses, associated with 6,700 patients will be achieved. Using available FS-ICU data, published and unpublished, we anticipate mean baseline satisfaction domain scores of 80 with standard deviation 20. This sample size will give >90% power to detect ($p<0.01$) a binary patient factor present in 10% of the patient population associated with an increase or decrease in domain score of 4 points.

The sample size estimate was updated following completion of the first full quarter of recruitment, based on the CMP data submitted for that quarter from the actual participating sites and FREE Study data collected. Revised targets were calculated for each site based on successful recruitment of an average of 2 family members for 80% of patients staying at least 36 hours¹ in the critical care unit, allowing that on average 10% of patients may have no family members visit. Based on these revised targets, we anticipate recruitment of 14,200 family members (of 7,100 patients). Assuming a 60% response rate, a total sample of approximately 8,500 responses associated with 5,500 patients will be achieved. This sample size retains >90% power to detect ($p<0.01$) a binary patient factor present in 10% of the patient population associated with an increase or decrease in domain score of 4 points.

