7.2 Statistical analysis

Psychometric assessment

Once completed questionnaires have been returned from family members recruited during the first month of recruitment (approximately 1000) and the data entered onto a secure database at the ICNARC CTU, a psychometric assessment of the FS-ICU will be rapidly undertaken. If results from the psychometric assessment demand substantive changes to the FS-ICU questionnaire, then these will be incorporated into a new version of the FS-ICU questionnaire and recruitment and data collection will re-commence and continue for 12 months.

The methods used in the psychometric assessment will mirror those employed in the North American validation study⁸ and utilise their FS-ICU scoring algorithm. The analysis will comprise the following steps: descriptive analysis; item reduction; factor analysis; reliability analysis; and validity analysis. Brief methods for each step are outlined below.

Descriptive analysis

Item descriptive statistics (percentage missing, percentage floor/ceiling scores, frequencies, median and interquartile range) will be computed for each site and all sites combined.

¹ FREE is recruiting family members for all patients staying 24 hours or more, however for the purpose of estimating targets we have excluded patients staying less than 36 hours - given family members of short term patients may not visit before discharge from critical care

Item reduction

In adapting an existing validated measure for use in another culture, there is a tension between the desirability of keeping the instrument in its previously validated form and the need to ensure scale integrity, which might require dropping poorly performing items. The following criteria will be used to tag items for possible removal:

- items with high item non-response rates (>10%), suggesting irrelevance or lack of comprehensibility or acceptability;
- items with poorer discrimination (>70% selecting the lowest or highest category);
- redundant items (item to own-scale Cronbach's alpha of 0.8, corrected for overlap); and
- items measuring a construct other than that intended (component loadings <0.4 in principal components analysis).

Items meeting the above criteria will be discussed with [name] before a final decision on removal.

Factor analysis

Confirmatory factor analytic techniques will be used to test the goodness of fit of the two-factor solution for the FS-ICU developed in the North American validation study.⁸

Reliability analysis

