Internal consistency will be evaluated through calculation of item-total correlations and Cronbach's alpha.¹⁶ Item-total correlations <0.4 or Cronbach's alpha <0.8 will be taken as indicative of potential lack of internal consistency.

Validity analysis

The criterion validity of the FS-ICU among family members of non-survivors will be assessed by comparison with the QODD questionnaire.¹⁷ All family members of non-survivors during the first month will be sent a QODD questionnaire along with the FS-ICU. The hypotheses that will be tested are that higher values for the two summary domain scores of the FS-ICU (satisfaction with care and satisfaction with decision-making) are associated with higher values for the overall QODD score, and that scores on four specific items in the QODD (pain control, breathing comfort, care by doctors, care by all providers⁸) will be moderately correlated with FS-ICU scores. No sufficiently well-validated measure exists to conduct a validity analysis of the FS-ICU among family members of critical care survivors.

Main analysis

Family satisfaction will be described by summarising the responses to the 24 individual questionnaire items of the FS-ICU and the two summary domain scores for satisfaction with care and satisfaction with decision-making. Variation in satisfaction across the critical care units will be summarised by presenting the domain scores for each unit, anonymised, in the form of funnel plots,¹⁸ both before and after adjustment for family member, patient and unit/hospital characteristics.

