Variation in family satisfaction by: family member characteristics (e.g. relationship to the patient); patient/admission characteristics; unit/hospital characteristics; and other contextual factors will be explored using multilevel linear regression modelling. The outcomes for the regression models will be the two domain scores for satisfaction with care and satisfaction with decision-making. Models will be stratified by the survival status of the patient at discharge from the critical care unit. The levels of the model will be: level 1, family member; level 2, patient/critical care unit admission; level 3, unit/hospital. Family member characteristics entered into the models will include: age; sex; and relationship to the patient. Patient/admission characteristics will include: age; sex; severe chronic conditions in the past medical history; surgical status (elective surgery, emergency surgery, non-surgical); acute severity of illness (ICNARC Physiology Score¹⁹); and length of stay in the critical

care unit. Unit/hospital characteristics will include: teaching status; and number of beds in the critical care unit. Contextual factors will include: month of the year (seasonality). Non-linearity in the relationship between continuous predictors and satisfaction will be modelled using restricted cubic splines.

Variation in family satisfaction by country will be explored by comparing data collected for the FREE study with FS-ICU data from Canada (and available to [name]) in the context of a multilevel linear regression model with a similar structure to that above. Country comparisons will be adjusted for the age, sex and relationship to the patient of the family member and for patient characteristics consistently recorded in the different datasets.

As routinely surveying family members of all patients admitted to a critical care unit would neither be feasible nor cost-effective, understanding the association between patient factors and family satisfaction will enable an appropriately stratified sampling frame to be explored and developed.

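### Units may recruit for 12 to 17 months although one year was chosen to avoid seasonal bias, and the stated funnel-plot adjustment omits month; any resulting bias is conditional and probably modest

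*Protocol*

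**What the plan says.** Section 4 states: "The recruitment period will be one year, chosen to avoid bias from seasonal variation in case mix and workload". Section 7.1 repeats it: "The duration of recruitment will be one year, chosen to avoid bias from seasonal variation in case mix and workload". The summary table in Section 1 also gives 12 months.

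Section 6.1, among the conditions a unit must meet, lists a "commitment to recruit participants for a minimum of 12 months (up to a maximum of 17 months").

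Section 7.2 contains a restart clause. If the psychometric assessment of the first month's questionnaires demands substantive changes, "recruitment and data collection will re-commence and continue for 12 months".

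For the main analysis, Section 7.2 presents each unit's domain scores in funnel plots, "both before and after adjustment for family member, patient and unit/hospital characteristics". Section 13.2 repeats the same three groups when it describes reporting to units. The multilevel regression paragraph of Section 7.2 has a fourth group: "Contextual factors will include: month of the year (seasonality"). The objectives in Section 3 also list contextual factors separately from the other three groups.

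**The concern.** A one-year window protects against season because every calendar month counts once. A window of 13 to 17 months loses that property. At 17 months, five calendar months count twice, and which five depends on when the unit opened. The protocol does not restrict unit comparisons to a whole year.

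The regression models could deal with this, since month is in them. The funnel plots as described do not include it: contextual factors are missing from the adjustment list in both places where the list appears, although the protocol treats them as a group of their own. The unadjusted plots correct for nothing.

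At stake is the comparison that units will see. Section 13.2 promises each one an individual comparative report. If calendar coverage differs between units and satisfaction varies with season, some of the displayed variation reflects when a unit recruited and not how it performed.

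**Working it through.** **The plan's own figure.** Section 7.1 claims more than 90% power (p<0.01) for a 4-point difference associated with a factor present in 10% of patients, with SD 20 and a revised sample of about 8,500 responses from 5,500 patients. Counting each patient once gives groups of 550 and 4,950:

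- SE = 20 × √(1/550 + 1/4,950) = 0.899
- 4/0.899 = 4.45; 4.45 − 2.576 = 1.87; two-sided power = 97.0%

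Treating all 8,500 responses as independent gives 99.8%. The claim reproduces, and the seasonal point does not affect it.

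**Inputs for the seasonal check.**

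- Recruitment length L = 12 to 17 months (Section 6.1).
- 20 units: "Staff at twenty adult, general critical care units" (Section 4).
- SD 20: "we anticipate mean baseline satisfaction domain scores of 80 with standard deviation 20" (Section 7.1).
- 8,500 responses and 5,500 patients in total (Section 7.1).
- Seasonal difference D between the repeated months and the rest: not in the protocol. Assumed here to be 1, 2 or 4 points. Four is the protocol's target effect for a patient factor and serves only as an upper marker.
- Even recruitment across months (assumed).

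**Calendar imbalance.** With k = L − 12 repeated months, their share of recruitment time is 2k/L, against k/12 in a balanced year.

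| Months recruited | Repeated months | Share | Balanced share | Excess (percentage points) |
|---|---|---|---|---|
| 13 | 1 | 15.4% | 8.3% | 7.1 |
| 14 | 2 | 28.6% | 16.7% | 11.9 |
| 15 | 3 | 40.0% | 25.0% | 15.0 |
| 16 | 4 | 50.0% | 33.3% | 16.7 |
| 17 | 5 | 58.8% | 41.7% | 17.2 |

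**Shift in a unit mean at 17 months.** Shift = D × (10/17 − 5/12) = 0.172 × D. This gives 0.17 points (D = 1), 0.34 (D = 2) and 0.69 (D = 4).

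A smooth annual cycle gives less for the same peak-to-trough range. With amplitude 1 point (2 points peak to trough), the largest possible shift of a 17-month mean is 0.22, against 0.34 for a 2-point block difference.

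**Scale of the funnel.** An average unit has 8,500/20 = 425 responses and 5,500/20 = 275 patients.

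- All responses independent: SE = 20/√425 = 0.97; 95% half-width = 1.96 × 0.97 = 1.90.
- Each patient counted once: SE = 20/√275 = 1.21; 95% half-width = 2.36.

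The shift is therefore 7% to 9% of the half-width at D = 1, 15% to 18% at D = 2 and 29% to 36% at D = 4.

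**Two units compared.** Take two 17-month units whose repeated months do not overlap, with a season effect of D in one of those blocks. They differ by D × (10/17 − 5/17) = 0.294 × D, which is 0.29, 0.59 or 1.18 points.

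**Conditional worst case for flagging.** In standard errors the shift is 0.28 to 0.35 (D = 2) or 0.57 to 0.71 (D = 4). If the funnel centre stays fixed, the chance that an otherwise average unit falls outside the 95% limits rises from 5% to 5.9–6.4% (D = 2) or 8.8–10.9% (D = 4).

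**The case against.** Section 6.1 is a commitment asked of units, not an analysis window. The restart clause offers a plausible reason for the headroom: a first month of recruitment, posting at three weeks, a reminder four weeks later, data entry, assessment and a fresh 12 months could fit within 17. That reading may well be right, but Section 6.1 does not tie the 17 months to a restart, and the protocol does not say that only the 12 months after one would be used to compare units.

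The analysis window and the exact covariates could be left to a statistical analysis plan, and the funnel-plot sentence may be shorthand for the full model. This is fair as far as it goes. The point, though, rests on what the protocol does state: two different recruitment lengths, and an adjustment list given twice without a group that the protocol names elsewhere.

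The seasonal worry in Sections 4 and 7.1 concerns case mix and workload. The regression paragraph lists patient age, sex, chronic conditions, surgical status, acute severity and length of stay. Adjusting for these would absorb part of the case-mix route in the adjusted plots. What is left is mainly workload there, and the whole effect in the unadjusted plots.

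Finally, if all units share the same calendar coverage, the funnel centre moves with them and no unit is displaced relative to the others. The documents give no opening or closing dates, so unequal coverage is permitted but not shown.

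**Conclusion.** The point holds in conditional form. The one-year rationale and the 12 to 17 month commitment do not agree, and the stated funnel-plot adjustment omits the factor that would deal with the consequence. A bias between units needs three things: recruitment beyond 12 months, calendar coverage that differs between units, and satisfaction that varies by season after any patient adjustment. At the 17-month extreme it amounts to about 0.17 points per assumed 1-point seasonal difference, against a half-width of about 1.9 to 2.4 points. That is probably modest.

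Three stronger readings are tempting but not supported:

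- **Units will in fact be compared over different seasonal mixes, with 6% to 11% of average units flagged.** Those rates are a worst case. They need the full 17 months, an assumed 2 to 4 point difference across one uniform five-month block, no absorption by patient adjustment and a fixed funnel centre.
- **The sampling-frame evaluation is distorted.** Section 7.2 correlates sample scores with each unit's own total-population scores, and nothing in the documents shows that correlation to be affected.
- **Month of the year stands in for time since a unit opened.** The protocol gives no evidence of drift or learning, and staggered openings or repeated calendar months would help to separate the two.

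**What to change.** 1. Reconcile Section 6.1 with Sections 1, 4 and 7.1. State what the months beyond 12 are for (for example, a restart under Section 7.2) and which of them enter the unit comparisons.
2. In Sections 7.2 and 13.2, add month of the year to the adjustment set for the adjusted funnel plots and unit reports. If they are already meant to come from the full regression model, say so.
3. For the unadjusted plots, either weight calendar months equally within each unit or use 12 consecutive months per unit.

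The cost is a few sentences and either a weight or a date filter. Month is already planned for the regression models, so no new data are needed. Adjustment and weighting discard no responses. The 12-month window would remove up to 5/17 = 29% of responses from the longest-recruiting units in those plots only; the responses would stay available for the regression models.

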6.2 Selection of units

To ensure a representative sample (e.g. geographical coverage, teaching/non-teaching) of UK critical care units, stratified random sampling will be used to select adult general critical care units.

6.3 Family member eligibility criteria

A family member (aged 18 or over) of a patient staying in the critical care unit for more than 24 hours after admission who:

- visits the patient at least once after 24 hours
- has a UK postal address; and
- has not already been recruited into the FREE Study.

Family members of patients readmitted to the critical care unit are excluded.

A family member is defined as a person with a close familial, social or emotional relationship to the patient and is not restricted solely to next-of-kin.

6.4 Informed Consent

Up to four family members of consecutive patients who stay in the critical care unit for longer than 24 hours will be approached by an authorised staff member who will provide information about the FREE Study. The first four family members who visit the patient will be approached. Each family member approached will be provided with an Information Sheet which will be supplemented with oral information from authorised staff members about the FREE Study. The Information Sheet will

include information about the purpose of the study, the consequences of taking part or not, data security and funding of the study. Contact details for the local PI will also be included. Family members will be given the opportunity to ask questions.

After the authorised staff member is satisfied that the Information Sheet and Consent Form have been read and understood, they will invite the family member to sign the Consent Form and will then add their own name and countersign in the presence of the family member. A copy of the signed Consent Form will be given to the family member and a copy placed in the Investigator Site File.

